The etiology of temporomandibular disorders is multifactorial. It includes trauma (such as traumatic injuries from eating, wide jaw opening, and dental management), bruxism (refers to a non-functional grinding and clenching of the teeth), malocclusion (causes inappropriate pressure on the joint), Stress and psychiatric illness. TMD is clinically characterized by pain in the temporomandibular region or in the muscles of mastication, pain radiating behind the eyes, in the face, shoulder, neck and/or the back, headaches, ear-ache or tinnitus, jaw clicking, locking or deviation, limited jaw opening, clenching or grinding of the teeth, dizziness and sensitivity of the teeth lacking oral disease. Pain is the most frequent symptom for

which patients seek medical attention.⁽⁸⁾

Internal derangement of the temporomandibular joint (TMJ) is one of the most common temporomandibular disorders. In 1983, Dolwick⁽⁹⁾ defined it as an abnormal relation between the temporomandibular disc with respect to the mandibular condyle, the temporal fossa, and the temporal eminence of the TMJ. Anterior disc displacement, with or without reduction, perforation of the retrodiscal tissue or the articular disc, and degenerative changes of the disc and/or the joint surfaces, may be present. Clinically, it may be accompanied by pain, limitation of mouth opening, clicking, and locking.⁽¹⁰⁾

In 1989, Wilkes⁽¹¹⁾ first established a classification to correlate clinical and radiological signs with surgical findings. The Wilkes classification consists of 5 stages based on clinical, radiologic, and intraoperative findings as follows:

Stage	Clinical Findings	Radiologic Findings	Surgical Findings
I	Painless clicking No locking No restricted motion	Slight anterior disk displacement that reduces on opening Normal osseous contours	Normal disk form Slight anterior disk displacement
II	Occasional painful clicking Intermittent locking Headaches	Slight anterior disk displacement that reduces on opening Early disk deformity Normal osseous contours	Thickened disk Anterior disk displacement
III	Frequent pain Joint tenderness Headaches Locking Restricted motion	Anterior disk displacement that does not reduce on opening Moderate disk deformity Normal osseous contours	Disk deformed and displaced Variable adhesions No bone changes

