According to Murakami on the rationale of arthroscopic surgery of the TMJ, he stated that, although various arthroscopic disc repositioning and suturing techniques were reported, the success rate was comparable to arthroscopic lysis and lavage, and the documentation by postoperative imaging was insufficient.⁽²⁴⁾

According to Israel: Numerous intra-articular operative arthroscopic techniques have been reported in the literature since the advent of temporomandibular joint (TMJ) arthroscopy. However, Ideal randomized controlled trials regarding outcomes are lacking nor are their strong evidence supporting one operative technique over another.⁽¹⁵⁾

Nowadays, minimally invasive procedures have eliminated the use of many of the more complex surgical procedures. Despite such advancements, however, clinicians are still encountering some difficulty in successfully treating many of these patients and finding the answers to these problems will

depend on future developments.

A review of the literature reveals that there is lack of randomized clinical trials to compare between the three levels of TMJ arthroscopy in the management of TMJ internal derangement.

The null hypothesis states that there will be no significant difference between the three levels of TMJ arthroscopy. Consequently, by doing the necessary studies and comparing the results, we can accept or reject this theory to finally develop guidelines and standardized patient selection criteria that can be followed by all researchers.

AIM OF THE STUDY

To compare between the three levels of TMJ arthroscopy in the management of TMJ internal derangement in the following points:

Primary aims are to assess:

1. Pain score using the visual analog score (VAS).⁽²⁵⁾
2. Presence or absence of clicking.
3. Mouth opening measuring the maximal interincisal opening in MIS.
4. Lateral excursion movement.
5. Protrusive movement.

[figure not shown]
Secondary aims are to assess:

1. Operative time.
2. Post operative MRI (disc position).

CONSORT

TRANSPARENT REPORTING of TRIALS

Study design

This study will be a randomized controlled clinical trial, with 1:1:1 ratio and will be reported according to CONSORT guidelines ⁽²⁶⁾

PICO Question

Do patients with TMJ internal derangement treated with arthroscopy level I compared to arthroscopy level II or arthroscopy level III show better maximal interincisal opening and less pain?

Settings and Location:

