Participants will be selected from the Maxillofacial and Plastic Surgery Department, Faculty of Dentistry, Alexandria University, Egypt.

Sample size calculation

The size was estimated based on 5% alpha error and 80% study power. The mean (SD) improvement in Maximum Interincisal Opening (MIO) after 6 months compared to the preoperative measurements was 6.09 (7.05) mm for Level I arthroscopy, (10) 6.7 (5.25) mm for Level II arthroscopy, ⁽²⁷⁾ and 18.5 (2.1) mm for Level III arthroscopy. ⁽²⁸⁾ Based on difference between independent means using F test and pooled SD = 4.8 mm, the minimum sample size was calculated to be 9 joints per group, increased to 10 joints to make up for lost to follow up cases. Total sample = number per group x number of groups = 10 x 3 = 30 joints. Sample size was based on Rosner's method ⁽²⁹⁾ calculated by G*Power 3.1.9.7. ⁽³⁰⁾

Randomization

Participants will be randomly assigned using online program (www.random.org) in order to allocate participants to the group.

Allocation Concealment

Sequentially numbered opaque sealed envelopes will be used to conceal allocation. One set of envelopes will be created to guarantee they were opaque, sealed and sequentially numbered.

Blinding

The patients will be blinded to the treatment group.

Intervention

Group I: 10 patients will be treated with level (I) arthroscopy (Lysis and lavage).

Group II: 10 patients will be treated with level (II) arthroscopy (operative arthroscopy).

Group III: 10 patients will be treated with level (III) arthroscopy (operative arthroscopy + disc repositioning and fixation).

Eligibility Criteria

Inclusion criteria

The patients with TMJ internal derangement will be divided into 5 stages according to Wilkes Classification.⁽¹¹⁾ Only patients with stage III will be

included in this study.

Exclusion criteria

1. Medically unfit patients.
2. Patients with TMDs secondary to malocclusion.
3. Psychological instability.
4. Patients operated before for other TMJ problems.

Materials

In all procedures, 1.9 mm, 30-degree optical device, sleeves, sharp and blunt trocars, adhesion knives, an exploratory probe, a bipolar electrode (Karl Storz Endoscopy, Tuttlingen, Germany) and coblator.

A specific material for pin placement is A third custom-made cannula (2.7mmdiameter) with a distal parallel double window (10 _ 2 mm) for direct view control of pin fixation, a long 1.5-mm rotatory drill for perforating disc and condyle, and an impactor with hammer (fixation kit).

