After the anterior release is completed, the obturator is positioned at the anterior margin of the disc and the disc is pushed backwards. The obturator slides along the surface of the disc and arrives in the posterolateral recess. The retrodiscal tissue is pushed down inferiorly and posteriorly.

7- Disc fixation: (Level III)

A disc fixation can be accomplished in 1 of 2 ways. The first and more traditional way is the suture discopexy. A second way is by rigid fixation with either resorbable or titanium screws. Regardless of the methodology of fixation, the disc is held in reduction during the course of the fixation. The target area of fixation is the posterior lateral corner of the disc-condyle assembly, the area of the lateral pole where the disc attaches to the condyle.

Postoperative management

Antibiotics and nonsteroidal anti-inflammatory drugs are routinely prescribed for 5 days. The softness of the postoperative diet should be decreased slowly. Exercises to improve mouth opening are explained to the patient and start 1 week after operation.

In patients with significant postoperative occlusal changes, a splint is recommended. It is designed to raise the bite and prevent contact between upper and lower incisors and canines. Due to the resulting distalization of the bite force, joint loading is reduced, which contributes to the joint's rehabilitation. The appliance should be left in place around the clock during the first ten postoperative days, then used at night for four additional weeks.⁽³⁴⁾

Follow up

- Pain assessment using VAS (Visual Analogue Scale) ⁽²⁵⁾

- Clicking (improvement or persistence).
- Range of motion ⁽³³⁾ including: maximal interincisal opening, lateral excursion movement and Protrusive movement
- Post-operative MRI at 6 months for detection of disc position.
- All patients will be followed up at 1, 3, 6 months.

ETHICAL CONSIDERATIONS

Research Ethics Committee approval

The research protocol will be approved by the Research Ethics Committee of Alexandria University Faculty of Dentistry (IRB No. 001056 – IORG 0008839) prior to any research-related activities

All research activities involving human subjects will abide with the Declaration of Helsinki ⁽³⁴⁾ and other ethical guidelines adopted by the Research Ethics Committee of Alexandria University Faculty of Dentistry.

The benefits to the participant and/or the community

1. Treatment of patients with internal derangement with minimally invasive surgery (TMJ arthroscopy).

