2. Short hospital stay with early recovery and rapid return to work.

The risks to the participant and/or the community

1. The need for long-term follow-up postoperative.
2. The exposure to radiation in MRI which is needed for follow-up at 6 months.

Anonymity and Confidentiality

The anonymity and confidentiality of the participants will be preserved by not revealing their names and identity in the data collection, analysis and reporting of the study findings.

The identity of participants will be kept confidential or anonymous and the assurances extend beyond protecting their names to also include the avoidance of using self-identifying statements and information.

DATA MANAGEMENT & STATISTICAL ANALYSIS

Data will be collected and analyzed statistically using ANOVA test to compare between the three groups.

REFERENCES

2. Thapliyal GK. Peterson's Principles of Oral & Maxillofacial Surgery. *Med J Armed Forces India.* 2006;62(1):89-.

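### One ANOVA sentence covers every outcome: the continuous primary aims have no stated response variable or baseline adjustment, and clicking has two codings and no categorical analysis

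*Combined protocol and SAP*

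**What the plan says.** Under Data Management & Statistical Analysis the whole plan reads "Data will be collected and analyzed statistically using ANOVA test to compare between the three groups". No other method is named anywhere in the document.

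Aim of the Study lists five primary aims: VAS pain, clicking, maximal interincisal opening (MIO), lateral excursion and protrusion. Follow up sets visits at 1, 3 and 6 months and names none as primary. The nearest thing to a response variable is in Sample size calculation, which rests on "improvement in Maximum Interincisal Opening (MIO) after 6 months compared to the preoperative measurements". The inputs there run from "6.09 (7.05) mm for Level I arthroscopy" through 6.7 (5.25) mm for Level II to "18.5 (2.1) mm for Level III arthroscopy", each from a different cited study.

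The PICO Question is pairwise in form: whether "arthroscopy level I compared to arthroscopy level II or arthroscopy level III show better maximal interincisal opening and less pain".

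Clicking is "Presence or absence of clicking" in the primary aims but "Clicking (improvement or persistence" in the Follow up list. Only stage III joints are eligible. The clinical findings for that stage in the Introduction's staging table are "Frequent pain Joint tenderness Headaches Locking Restricted motion"; clicking is not listed.

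**The concern.** A plan that names a test but not the variable tested leaves the main analytical choice open until the data are in. Change from baseline and the 6-month value are both legitimate, and in the same patients they can give different answers. The preoperative value enters the sizing of MIO but no planned analysis adjusts for it, although baseline adjustment would settle the choice.

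The ANOVA also stops short of the pairwise comparison that the PICO Question asks about. If pairwise contrasts follow, how their error term is formed matters when the arm SDs differ as much as the sizing inputs do.

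For clicking, the Follow up coding has no value for a joint that did not click before surgery, or for one that starts to click afterwards. The two codings therefore have different denominators. A mean comparison also gives no planned effect measure for a yes/no outcome.

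**Working it through.** **The plan's own figure.** The pooled SD of 4.8 mm is the simple mean of the three SDs: (7.05 + 5.25 + 2.1)/3 = 14.4/3 = 4.8. The root-mean-square value is 5.22. With means 6.09, 6.7 and 18.5 (average 10.43), the SD of the means is sqrt[(4.34² + 3.73² + 8.07²)/3] = 5.71, so f = 5.71/4.8 = 1.19. The F test then needs 4 per group (power 0.88), so the stated 9 is not reproduced (power at 9 is 0.9997). That is a separate matter; nothing below depends on it. It does show that the sizing variable was 6-month change in MIO.

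**Open response variable.** Assumptions: 10 per arm, no true difference, equal SDs before and after and across arms, pre/post correlation r. The documents give no r, so 0.3 to 0.7 is assumed. Results from 40,000 simulated trials per setting:

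| r | Change or follow-up ANOVA significant | The two disagree |
|---|---|---|
| 0.3 | 9.0% | 8.0% |
| 0.5 | 9.2% | 8.4% |
| 0.7 | 9.5% | 8.9% |

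Either analysis alone rejects in about 5%.

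**What adjustment gains with equal SDs.** Error variances relative to the raw variance are 2(1 - r) for change, 1 for follow-up only and 1 - r² for ANCOVA. Hence ANCOVA/change = (1 + r)/2 = 0.65, 0.75, 0.85, and ANCOVA/follow-up = 1 - r² = 0.91, 0.75, 0.51, for r = 0.3, 0.5, 0.7.

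**If arm SDs differ as in the sizing inputs.** Take 7.05, 5.25 and 2.1 mm as SDs of change, 10 per arm, no true difference. For Level I v II:
- The true standard error is sqrt[(7.05² + 5.25²)/10] = 2.78 mm.
- Error pooled over all three arms implies about sqrt(2 × 5.22²/10) = 2.33 mm, which is too small because Level III pulls it down.

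| Procedure | Half-width of 95% interval, I v II | False positives |
|---|---|---|
| Unadjusted contrast, error pooled over three arms | 4.7 mm | about 10% |
| Tukey after the ANOVA | 5.7 mm | about 5% |
| Welch on change | 5.8 mm | about 5% |
| Planned three-group F test (omnibus) | not applicable | about 6% |

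Randomised arms share one baseline distribution in expectation. With an assumed common baseline SD of 5 mm and change independent of baseline, ANCOVA with a variance-robust (HC3) interval gives ±6.1 mm and about 4% false positives, against ±5.8 mm for Welch on change. The true slope on baseline is then 1, so adjustment has nothing left to remove beyond subtraction, and it costs a degree of freedom.

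**Clicking.** By full enumeration of the three-arm tables, ANOVA on 0/1 data has a maximum type I error of 5.0% at 10 per arm and 5.8% at 9. Power at 10 per arm, at assumed rates:

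| Rates, Levels I/II/III | ANOVA | Unconditional exact | Fisher-Freeman-Halton |
|---|---|---|---|
| 10/10/40% | 39% | 32% | 27% |
| 50/50/10% | 48% | 48% | 45% |

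The coding can matter more than the test. As an invented illustration, suppose 5 of 10 joints click before surgery in each of two arms. In Level I, 2 persist and none are new: presence 2/10 = 20%, persistence 2/5 = 40%. In Level III, 1 persists and 3 are new: presence 4/10 = 40%, persistence 1/5 = 20%. The ranking reverses with the coding.

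**The case against.** The strongest reply is that the sizing already fixes 6-month change, that the Introduction states the null hypothesis as no difference between the three levels, which is what the ANOVA tests, and that ANOVA behaves acceptably here. Much of this stands. For MIO, change at 6 months is a fair inference. The planned F test rejects in about 6% even with the unequal sizing SDs. But the inference covers one of four continuous aims, and the analysis section does not adopt it.

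Three stronger readings are tempting and are not supported:

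- A reader might infer that pairwise comparisons after this ANOVA have 10% false positives. That figure belongs to one procedure that the plan does not name. Tukey gives about 5% for Level I v II. The SD spread also comes from three separate studies and may reflect their populations rather than the arms of this trial.
- A reader might infer that ANCOVA always narrows the intervals. The 65-85% ratio needs equal SDs; with the sizing SDs the interval for Level I v II may be slightly wider.
- A reader might infer that ANOVA on clicking inflates false positives, or that stage III joints do not click. The enumeration does not show material inflation. The staging table omits clicking for stage III but does not say it is absent.

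**Conclusion.** The point holds as a matter that should be fixed before outcome data are seen. What the text itself shows is firm: one ANOVA sentence, no response variable or visit, no use of the preoperative value, two clicking codings and no categorical method.

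The sizes are conditional. The rise from 5% to about 9% assumes that both response variables are tried, with equal SDs and r between 0.3 and 0.7. The precision gain rests on the same equal-SD assumption and may vanish for Level I v II. For clicking the harm is the lack of a single usable endpoint and effect measure, not a raised error rate. How many joints would lack a value under the second coding cannot be known from the documents.

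**What to change.** Replace the analysis sentence with:

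> MIO, VAS, lateral excursion and protrusion at 6 months will be compared by ANCOVA with group as factor and the preoperative value as covariate; pairwise differences will be given with 95% confidence intervals that do not assume equal variances across arms. Clicking will be recorded as present or absent before surgery and at each visit; presence at 6 months will be compared by an exact test (Fisher-Freeman-Halton or unconditional, chosen in advance), with risk differences and 95% confidence intervals. Disc position on MRI, if recorded as a category, will be compared in the same way.

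Operative time has no preoperative value and can keep a three-group comparison of means; one line should say so.

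Confirm that all four continuous measures and clicking are recorded before surgery, because Pre-surgical evaluation does not itemise them. Sample size calculation counts joints and the Abstract counts patients, so use one joint per patient or account for clustering. This wording does not settle multiplicity across five primary aims.

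Cost: one paragraph, one clicking field per visit including before surgery, and a check of the preoperative form; no extra patients or visits. Downsides: one degree of freedom for the covariate; possibly slightly wider intervals when arm variances differ strongly (about ±6.1 v ±5.8 mm in the setting above); and some loss of power for clicking (39% to 32% or 27% at assumed rates of 10/10/40%).
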